9. ETHICAL CONSIDERATIONS

9.1 Declaration of Helsinki and IRB Approval

This study will be conducted in full compliance with the ethical principles of the Declaration of Helsinki and Good Clinical Practice (GCP) guidelines. The protocol, informed consent form, and all associated materials will be reviewed and approved by the local Institutional Review Board (IRB) / Helsinki Committee prior to patient enrollment.

9.2 Risk and Benefit Assessment

The investigational component of the study consists solely of additional electrophysiological mapping performed using clinically approved electroanatomical mapping systems and catheters during a standard-of-care AF ablation procedure.

Risks: The primary risk specific to this study is the prolongation of the procedure by approximately 15 minutes to accommodate mapping with two separate catheters. This additional mapping time is purely electrophysiological and does not involve any additional fluoroscopy (radiation) exposure. Therefore, potential risks are those inherent to standard catheter ablation procedures and include, but are not limited to:

- cardiac tamponade
- stroke or transient ischemic attack
- vascular complications
- phrenic nerve injury

Benefits: Using two high-density catheters allows for an exceptionally thorough interrogation of the ablation lines. This heightened scrutiny increases the probability of detecting micro-gaps in the ablation line that a single map might miss. Any detected gaps will be treated immediately, potentially reducing the patient's risk of future arrhythmia recurrence. Furthermore, patients will benefit from rigorous, structured follow-up care for a full year. On a broader scale, this study will help establish optimized workflows for future patients.

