4. STUDY ENDPOINTS

4.1 Primary Endpoints

- **Concordance:** Percentage of agreement (presence vs. absence of bidirectional block) between the Optrell real-time vector assessment and standard activation remapping on a per-line basis.
- **Workflow Efficiency:** Difference in time (in minutes) required to confirm conduction block status using the Optrell vector method versus full activation mapping.

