6.2 Intra-Procedural Workflow

The procedure will be performed under general anesthesia. Following standard venous access, transseptal puncture will be performed to access the left atrium. Systemic anticoagulation with intravenous Heparin will be administered and maintained to achieve an activated clotting time (ACT) >300 seconds.

• Phase 1: Voltage Mapping (coronary sinus pacing)

Following transseptal access and prior to ablation, a left atrial 3D map using TPI with left atrial voltage mapping will be performed using the Octaray catheter. The Octaray catheter will then be exchanged for the Optrell catheter, and a second high-density voltage map will be acquired on the

same 3D map (remap). A high density Multipolar map using parallel mapping will be performed in the same time with the Optrell catheter. All the maps need to have a fill threshold $\leq 3\text{mm}$ to allow sufficient density.

For patient in atrial fibrillation, an electrical cardioversion will be performed and mapping will be performed during coronary sinus pacing. For patient in sinus rhythm, mapping will be performed during coronary sinus pacing. For patient in atrial flutter, mapping will be performed in arrhythmia.

• **Phase 2: Ablation:**

The operator will perform PVI and any clinically indicated linear lesion sets according to standard of care using either radiofrequency or pulsed field ablation energy.

• **Phase 3: Conduction Block Assessment**

After completing the ablation phase, conduction block across lines will be assessed using both methods:

- *Optrell Vector Assessment*: Real-time evaluation of conduction vectors using the Optrell catheter and V8 software. The time to determination, from the beginning of the mapping (pacing start) to block confirmation, and the binary result (block vs. no block) will be recorded.
- *Standard Activation Mapping*: Creation of a full activation map using the Octaray catheter (often requiring pacing maneuvers) to establish the gold-standard confirmation of block. Time to determination, from the beginning of the mapping to block confirmation, and the binary result will be recorded.

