232 Continuation, initiation, or discontinuation of AAD therapy during follow-up will not be dictated
233 by the study protocol. All AAD use will be prospectively documented, including drug type, dosing,
234 changes, discontinuation, and replacement. This information will be incorporated into the clinical
235 database and considered in exploratory analyses of arrhythmia recurrence.

236

237 **7.4 Redo Procedures and Lesion Durability Assessment**

238 Any documented recurrence of atrial flutter or AF will prompt consideration for a redo procedure,
239 as clinically indicated.

240 If a redo procedure is performed during the 12-month follow-up period, the index protocol
241 performed again: a left atrial 3D map using TPI with left atrial voltage mapping will be performed
242 using the Octaray catheter. The Octaray catheter will then be exchanged for the Optrell catheter,
243 and a second high-density voltage map will be acquired on the same 3D map (remap). A high
244 density Multipolar map using parallel mapping will be performed in the same time with the Optrell
245 catheter. All the maps need to have a fill threshold ≤ 3 mm to allow sufficient density. For patient
246 in atrial fibrillation, an electrical cardioversion will be performed and mapping will be performed
247 during coronary sinus pacing. For patient in sinus rhythm, mapping will be performed during
248 coronary sinus pacing. For patient in atrial flutter, mapping will be performed in arrhythmia.

249 • **Block Assessment:** Prior to delivering any new ablation, the operator must re-assess
250 conduction block across all linear ablation lesions created during the index procedure.

251 **Gold Standard Block Assessment:** Creation of a full activation map using the Octaray catheter
252 (often requiring pacing maneuvers) to establish the gold-standard confirmation of block. Time to
253 determination, from the beginning of the mapping to block confirmation, and the binary result will
254 be recorded.

255 **Optrell Vector Assessment:** Real-time evaluation of conduction vectors using the Optrell catheter
256 and V8 software. The time to determination, from the beginning of the mapping (pacing start) to
257 block confirmation, and the binary result (block vs. no block) will be recorded.

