Optrell bipolar	 Yes  No	 Yes  No	_____ points
Optrell multipolar	 Yes  No	 Yes  No	_____ points

SECTION 3: PHASE 2 - ABLATION DETAILS

Variable	Data Entry
Ablation Energy Used	 RFA  PFA
PVI Performed?	 Yes  No
PVI Successfully Achieved?	 Yes  No
First Pass Isolation ?	 Yes  No
Linear Lesions Created (Check all that apply)	 Roof Line  Posterior Wall Isolation (PWI)  Cavotricuspid Isthmus (CTI)  Mitral Isthmus Line  Other: _____

SECTION 4: PHASE 3 - CONDUCTION BLOCK ASSESSMENT

(Complete this sub-section for EVERY linear lesion created. See Section 4b, 4c and 4d. Duplicate if necessary.)

Line Checked	 Roof Line  Posterior Wall Isolation (PWI)  Cavotricuspid Isthmus (CTI)  Mitral Isthmus Line  Other:	
Ablation Energy Used	 RFA  PFA	

Assessment Method	Time to Verify Block	Block Confirmed?
Optrell Vector Assessment (time to assess block by moving the catheter across the line to review vectors)	___ min : ___ sec	 Yes  No
Octaray Activation Mapping (time to create an activation map sufficient to determine presence or absence of block)	___ min : ___ sec	 Yes  No

Concordance for this line: ☐Yes (Methods agree) ☐No (Methods disagree)

Explain:_____

SECTION 5: ACUTE PROCEDURAL COMPLICATIONS (completed at hospital discharge)

Variable	Data Entry
None	
Pericardial Effusion / Tamponnade	
Stroke / TIA	

CONFIDENTIAL

Variable	Data Entry
Vascular Complication requiring intervention	
Phrenic Nerve Injury	
Prolongation of Hospitalization (>24 hours beyond the expected post-procedural course)	
Esophageal injury	

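### Phase 3 does not tie the two block readings of a line to the same lesion state, so touch-up ablation between them can turn two correct readings into a disagreement

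*Protocol*

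**What the plan says.** - **Endpoint (4.1, 8.2).** The first primary endpoint is per-line agreement between the two methods on whether bidirectional block is present. It is analysed as percentage agreement and Cohen's kappa. The second is the difference in time needed to establish block status.
- **Workflow (6.2, Phase 3).** "After completing the ablation phase, conduction block across lines will be assessed using both methods". The vector reading uses the Optrell catheter. The reference is a separate procedure: "Creation of a full activation map using the Octaray catheter (often requiring pacing maneuvers) to establish the gold-standard confirmation of block". The readings are therefore sequential. Phase 3 lists the vector reading first but fixes no order. It does not say whether ablation may fall between the readings, or which reading counts if a line is re-ablated.
- **Gaps (9.2, Benefits).** Mapping with two catheters "increases the probability of detecting micro-gaps in the ablation line that a single map might miss", and then: "Any detected gaps will be treated immediately".
- **Redo procedures (7.4).** For lines made at the index procedure: "Prior to delivering any new ablation, the operator must re-assess" conduction block. Section 6.2 has no counterpart for the index readings.
- **Data capture (Appendix D, Section 4).** "Complete this sub-section for EVERY linear lesion created". Each block holds one yes/no result and one duration per method, a concordance tick box and a free-text line for explanation. There is no field for reading order, clock time, ablation between readings or a repeat reading.

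**The concern.** A method-agreement statistic means something only if both methods looked at the same thing. Here the object can change between the two looks, and the wording of 9.2 invites that change at the moment the first method reports a gap. The affected lines are those with a gap. They are likely to be a minority, and kappa depends heavily on them.

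A later statistical analysis plan could not reliably repair this. If order and intervening ablation are not recorded as data, affected pairs can be found only where someone happened to write a note.

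The time endpoint is exposed in the same way. Section 6.2 runs each clock until block is confirmed, so on a line with a gap the time could include touch-up, or the two times could belong to different lesion states.

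**Working it through.** The protocol gives no figure to reproduce. The target of 30 patients is not derived, and neither the number of lines nor a gap rate is stated. What follows is an illustration on assumed inputs.

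**Inputs (all assumed)**
- g = share of lines with a gap at the first reading: 5, 10, 20, 30%.
- f = share of those gaps ablated before the second reading: 0, 50, 100%.
- s = touch-up success: 90%.
- Vector reading first, and both methods perfect, so any disagreement comes only from the change of lesion state.

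**Formulas.** Let d = g × f × s, the share of lines read as no block first and block second.
- Observed agreement: po = 1 − d.
- Share called block: first method 1 − g, second method 1 − g + d.
- Chance agreement: pe = (1 − g)(1 − g + d) + g(g − d).
- kappa = (po − pe)/(1 − pe).

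**Worked case, g = 30%, f = 100%.** d = 0.30 × 1 × 0.9 = 0.27, so po = 0.73. pe = 0.70 × 0.97 + 0.30 × 0.03 = 0.688. kappa = 0.042/0.312 = 0.135.

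| Gap share g | None ablated between | Half ablated between | All ablated between |
|---|---|---|---|
| 5% | 100%, kappa 1 | 97.8%, kappa 0.699 | 95.5%, kappa 0.174 |
| 10% | 100%, kappa 1 | 95.5%, kappa 0.688 | 91.0%, kappa 0.167 |
| 20% | 100%, kappa 1 | 91.0%, kappa 0.662 | 82.0%, kappa 0.151 |
| 30% | 100%, kappa 1 | 86.5%, kappa 0.631 | 73.0%, kappa 0.135 |

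**Limiting case.** If every gap is ablated between readings and every touch-up succeeds, d = g. Then po and pe both equal 1 − g, and kappa is 0 for any g.

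**Imperfect vector method** (assumed sensitivity for a gap 0.80, specificity 0.95, activation map taken as truth; true gaps that it finds are touched up at 90% success):
- 10% gaps: 93.5% and kappa 0.675 with no touch-up between; 89.9% and 0.416 with half; 86.3% and 0.062 with all.
- 20% gaps: 92.0% and 0.750; 84.8% and 0.451; 77.6% and 0.041.

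**Effect of simply dropping affected pairs.** Take the same imperfect method at 10% gaps, and suppose every line that it calls a gap is ablated before the second reading. Only lines that it calls block remain: 0.90 × 0.95 = 0.855 agreeing and 0.10 × 0.20 = 0.020 disagreeing. Agreement is 0.855/0.875 = 97.7%, against an undistorted 93.5%. Because every retained vector result is block, kappa is 0. Exclusion therefore has a bias of its own, in the other direction.

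**The case against.** The best defence is that 9.2 is a benefit statement in the ethics section, not a workflow step. It speaks of using two catheters and of gaps that one map might miss, which fits treatment after both maps are complete. Section 6.2 places both readings after the ablation phase, and 6.3 describes a single additional mapping sequence there. On that reading, immediately means within the same procedure. This is a fair reading and may be what was intended. But 6.2 does not state it, and 9.2 is the only text on when gaps found by the dual mapping are treated. The result is an ambiguity that permits the problem, not proof that it will occur.

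Other limits also stand:
- In the order that 6.2 lists, a gap missed by the vector method prompts no touch-up, so the miss is still captured. A false gap call on a blocked line is discordant either way. Only gaps correctly found by the first method are distorted, and that lowers agreement.
- A reader might infer that the endpoint could move in either direction with both methods perfect. It cannot: percentage agreement then starts at 100% and can only fall. Inflation would require a site to overwrite a recorded first result with the final state, and nothing in the protocol suggests that.
- A reader might infer that kappa collapses to zero. That needs every gap to be ablated successfully between readings.
- The CRF is not wholly silent, since the free-text line could hold a note on touch-up. That is weaker than a structured field and does not reliably identify the affected pairs.

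**Conclusion.** The point holds as a gap in the protocol's rules for conduct and data capture. As written, the index procedure can pair a reading before touch-up with one after it, score two correct results as disagreement, and leave no reliable trace. The direction is downward for agreement and kappa. The size cannot be known from the protocol: it runs from no effect (no ablation between readings) to the right-hand column of the table (all gaps ablated between readings), on assumed gap prevalence, perfect methods and 90% touch-up success. Percentage agreement falls moderately, while kappa can fall close to zero. The protocol does not show that this will happen or how often. It is still worth settling before the first patient, because it bears on a primary endpoint and information not collected cannot be recovered.

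**What to change.** 1. Reconcile 6.2 and 9.2 with each other and with the safeguard in 7.4, so that the protocol says how the two index readings relate to any touch-up. When to treat a gap remains the operator's decision; what is needed is a rule for the data.
2. In 6.2 and 8.2, define the primary pair, for both concordance and time, as the first reading by each method on the same lesion state. The first method's result and time are recorded before the second method starts.
3. In Appendix D, Section 4, add three fields: which method came first, the clock time of each reading, and whether that line was ablated between the readings (yes/no). Enter any re-reading after touch-up in a new block, without overwriting the first. The same fields are needed in the matching section of Appendix F if lines newly made at a redo enter the analysis.
4. Do not silently exclude pairs with intervening ablation, because they are selected for a gap found by the first method. Report their number and first-method result separately, and show agreement with and without them.

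The cost is a few CRF fields and some protocol wording, with no additional map or catheter. Some pairs may turn out not to be interpretable, and the report should say how many.

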9.3 Informed Consent

Written informed consent will be obtained from all eligible patients prior to any study-specific procedures. Patients will be thoroughly counseled regarding the use of both catheters, the anticipated 15-minute procedural prolongation, the lack of additional radiation, and the rigorous follow-up schedule.

10. STUDY GOVERNANCE AND SAFETY OVERSIGHT

An independent Data Safety Monitoring Board will not be established for this investigator-initiated observational study due to the limited sample size and the fact that the investigational component consists solely of additional electrophysiological mapping using commercially approved technologies within a standard-of-care ablation procedure.

Safety oversight will be performed by a designated Medical Monitor, who will review all reported acute procedural complications (e.g., cardiac tamponade, stroke or transient ischemic attack, and vascular complications requiring intervention) within 72 hours of occurrence.

If two or more unexpected severe adverse events potentially attributable to the repolarization mapping protocol occur within the first ten enrolled patients, study enrollment will be temporarily paused and an ad-hoc safety review will be conducted to determine whether protocol modifications are required before enrollment resumes.

Safety events and protocol adherence will be monitored throughout the study.

Study Registration: the study will be registered in a public clinical trials registry (e.g., ClinicalTrials.gov) prior to enrollment of the first patient, in accordance with International Committee of Medical Journal Editors (ICMJE) requirements.

11. STUDY MONITORING AND DATA PROTECTION

Study Monitoring

CONFIDENTIAL

The study will be conducted in accordance with ICH-GCP principles and applicable institutional policies. Monitoring will be performed using a risk-based approach appropriate for an investigator-initiated observational study. Monitoring activities may include on-site or remote review of study documentation.

[figure not shown]
Monitoring will verify:

- IRB / Ethics Committee approval
- informed consent documentation
- patient eligibility
- accuracy of key study variables
- documentation of adverse events
- protocol compliance

Data Protection

All patient data will be collected and stored in a pseudonymized format using a unique study identification number. Directly identifiable patient information will remain securely stored at the study site and will not be transferred outside the institution. Study data will be stored in secure institutional systems and handled in accordance with applicable data protection regulations, including GDPR where applicable. Study data will be retained for at least 10 years after study completion, or longer if required by institutional or national regulations. Access to the study database will be limited to study investigators and authorized research personnel.

12. APPENDIX A - STUDY FLOWCHART

13. APPENDIX B- Schedule of Assessments

Study Activity	Screening / Pre- Procedure	Procedure Day	Post-Procedure / Discharge	1 Month	3 Months	6 Months	9 Months	12 Months
Informed consent	-----X-----							
Eligibility confirmation	X	X						
Demographics and medical history	X							
Arrhythmia Classification (PAF / PerAF / Flutter)	X							
Baseline medications	X		X	X	X	X	X	X
Standard Ablation according to protocol		X						
Procedural safety assessment		X	X					
Adverse event assessment			X	X	X	X	X	X
ECG			X	X	X	X	X	X
AAD documentation			X	X	X	X	X	X
48-hour Holter					X	X		X
Arrhythmia recurrence assessment				X	X	X	X	X
Documentation of redo ablation (if applicable)					X	X	X	X

14. Appendix C – AE / SAE Form

Field	Description / Options
Study ID	
Hospital MRN	
Event number	
Event classification	 AE  SAE
SAE Category	
SAE type	 Pericardial effusion / tamponade  Stroke / TIA  Vascular complication requiring intervention  Phrenic nerve injury  Esophageal injury  Heart failure exacerbation requiring treatment  Prolonged hospitalization (>24h)  Other (specify)
Event description	
Date of onset	
Date of resolution	
Severity	 Mild  Moderate  Severe
Seriousness criteria	 Death  Life-threatening event  Prolonged hospitalization  Persistent disability  Medically significant event
Relationship to procedure	 Related to procedure  Possibly related to study mapping protocol  Unrelated
Action taken	 Observation  Medication  Intervention  Hospitalization  Other
Outcome	 Resolved  Ongoing  Resolved with sequelae  Death
Reported to Medical Mon	 Yes  No
Date reported	
Investigator signature	

15. Appendix D – Procedural CRF**SECTION 1: DEMOGRAPHICS AND CLINICAL HISTORY/DATA**

Variable	Data Entry
Date of Procedure	_____
Patient MRN	_____
Age / Gender	_____ years  Male  Female
Height	_____ cm
Weight	_____ kg
BMI	_____ kg/m ²
Type of Arrhythmia	 Paroxysmal AF  Persistent AF  Atrial Flutter : _____
Prior AF Ablation?	 No (De novo)  Yes (Redo) : _____
Operator 1 Operator 2	

CHA2DS2-VASc Score

Risk Factor	Points	Check if Present
Congestive Heart Failure	1	
Hypertension	1	
Age ≥75 years	2	
Diabetes Mellitus	1	

CONFIDENTIAL

Risk Factor	Points	Check if Present
Stroke / TIA / Thromboembolism	2	
Vascular Disease	1	
Age 65 - 74 years	1	
Sex Category (Female)	1	
TOTAL SCORE		____ / 9

Echocardiography Parameters

Variable	Entry
Date of Echo	____ / ____ / ____
LVEF (%)	_____
LA Diameter (mm)	_____
LA Volume (ml)	_____
LA Volume Indexed (ml/m ²)	_____
RA Enlargement	 None  Mild  Moderate  Severe
Mitral Regurgitation	 None  Mild  Moderate  Severe

Antiarrhythmic Drug (AAD) History

(Check all currently or recently used)

☐ Amiodarone ☐ Flecainide ☐ Propafenone ☐ Dronedarone ☐ Other: _____

SECTION 2: PHASE 1 - PRE-ABLATION MAPPING

(Both maps must be acquired during CS pacing or in arrhythmia if patient is in flutter, with a fill threshold 3mm)

Catheter	LA Map Completed?	Fill Threshold \leq 3mm Achieved?	Total Number of Points
Octaray	 Yes  No	 Yes  No	_____ points
Optrell bipolar	 Yes  No	 Yes  No	_____ points
Optrell multipolar	 Yes  No	 Yes  No	_____ points

Catheter	RA Map Completed?	Fill Threshold \leq 3mm Achieved?	Total Number of Points
Octaray	 Yes  No	 Yes  No	_____ points
Optrell bipolar	 Yes  No	 Yes  No	_____ points
Optrell multipolar	 Yes  No	 Yes  No	_____ points

SECTION 3: PHASE 2 - ABLATION DETAILS

Variable	Data Entry
Ablation Energy Used	 RFA  PFA
PVI Performed?	 Yes  No
PVI Successfully Achieved?	 Yes  No
First Pass Isolation ?	 Yes  No
Linear Lesions Created (Check all that apply)	 Roof Line  Posterior Wall Isolation (PWI)  Cavotricuspid Isthmus (CTI)  Mitral Isthmus Line  Other: _____

SECTION 4: PHASE 3 - CONDUCTION BLOCK ASSESSMENT

(Complete this sub-section for EVERY linear lesion created. See Section 4b, 4c and 4d. Duplicate if necessary.)

Line Checked	 Roof Line  Posterior Wall Isolation (PWI)  Cavotricuspid Isthmus (CTI)  Mitral Isthmus Line  Other:	
Ablation Energy Used	 RFA  PFA	

Assessment Method	Time to Verify Block	Block Confirmed?
Optrell Vector Assessment (time to assess block by moving the catheter across the line to review vectors)	___ min : ___ sec	 Yes  No
Octaray Activation Mapping (time to create an activation map sufficient to determine presence or absence of block)	___ min : ___ sec	 Yes  No

Concordance for this line: ☐Yes (Methods agree) ☐No (Methods disagree)

Explain:_____

SECTION 5: ACUTE PROCEDURAL COMPLICATIONS (completed at hospital discharge)

Variable	Data Entry
None	
Pericardial Effusion / Tamponnade	
Stroke / TIA	

CONFIDENTIAL

Variable	Data Entry
Vascular Complication requiring intervention	
Phrenic Nerve Injury	
Prolongation of Hospitalization (>24 hours beyond the expected post-procedural course)	
Esophageal injury	
Heart failure exacerbation requiring treatment	
Other :	

Form Completed By: _____ Date: _____

Investigator Signature: _____ Date: _____

SECTION 4b: PHASE 3 - CONDUCTION BLOCK ASSESSMENT

Line Checked	 Roof Line  Posterior Wall Isolation (PWI)  Cavotricuspid Isthmus (CTI)  Mitral Isthmus Line  Other:	
Ablation Energy Used	 RFA  PFA	

Assessment Method	Time to Verify Block	Block Confirmed?
Optrell Vector Assessment (time to assess block by moving the catheter across the line to review vectors)	___ min : ___ sec	 Yes  No
Octaray Activation Mapping (time to create an activation map sufficient to determine presence or absence of block)	___ min : ___ sec	 Yes  No

Concordance for this line: ☐Yes (Methods agree) ☐No (Methods disagree)

Explain: _____

SECTION 4c: PHASE 3 - CONDUCTION BLOCK ASSESSMENT

Line Checked	 Roof Line  Posterior Wall Isolation (PWI)  Cavotricuspid Isthmus (CTI)  Mitral Isthmus Line  Other:	
Ablation Energy Used	 RFA  PFA	

Assessment Method	Time to Verify Block	Block Confirmed?
Optrell Vector Assessment (time to assess block by moving the catheter across the line to review vectors)	___ min : ___ sec	 Yes  No
Octaray Activation Mapping (time to create an activation map sufficient to determine presence or absence of block)	___ min : ___ sec	 Yes  No

Concordance for this line: ☐Yes (Methods agree) ☐No (Methods disagree)

Explain:_____

SECTION 4d: PHASE 3 - CONDUCTION BLOCK ASSESSMENT

Line Checked	 Roof Line  Posterior Wall Isolation (PWI)  Cavotricuspid Isthmus (CTI)  Mitral Isthmus Line  Other:	
Ablation Energy Used	 RFA  PFA	

Assessment Method	Time to Verify Block	Block Confirmed?
Optrell Vector Assessment (time to assess block by moving the catheter across the line to review vectors)	____ min : ____ sec	 Yes  No
Octaray Activation Mapping (time to create an activation map sufficient to determine presence or absence of block)	____ min : ____ sec	 Yes  No

Concordance for this line: ☐Yes (Methods agree) ☐No (Methods disagree)

Explain:_____

16. Appendix E – Follow-Up CRF**SECTION 1: VISIT INFORMATION**

Variable	Data Entry
Date of Procedure	_____
Patient MRN	_____
Follow-Up Visit	 1 Mo  3 Mo  6 Mo  9 Mo  12 Mo
Visit Type	 In-Person  Virtual (Telehealth)
Visit Date	_____
Within protocol window?	 Yes  No (Protocol Deviation)

SECTION 2: RHYTHM STATUS & RECURRENCE

(Arrhythmia \geq 30 sec beyond blanking period of 2 months from last procedure)

Variable	Data Entry
Documented Atrial Arrhythmia Since Last Visit?	 Yes  No
Type of Arrhythmia Documented	 AF  AT  Typical Flutter  Atypical Flutter
Symptomatic During Episode?	 Yes  No
Date of First Recurrence	_____
Number of Episodes	 1  1-3  3-5  >5

SECTION 3: RHYTHM MONITORING

Variable	Data Entry
12-Lead ECG Performed?	 Yes (Date: _____)  No
ECG Result	 No Arrhythmia  AF  AT  Flutter
48-Hour Holter Performed?	 Yes (Date: _____)  No
Testing Location	 Hospital Clinic  Kupat Holim (Community)
Holter Result	 No Arrhythmia  AF  AT  Flutter

SECTION 4: CLINICAL EVENTS SINCE LAST VISIT

Variable	Data Entry
Hospitalization	 Yes  No
If Yes – Reason	 Arrhythmia  Heart Failure  Other CV  Non-cardiac
ER Visit	 Yes  No
DCCV Performed	 Yes  No

SECTION 5: MEDICATION STATUS

Variable	Data Entry
Currently on AAD?	 Yes  No
If Yes – AAD Used	 Amiodarone  Flecainide  Propafenone  Dronedarone  Other : _____
AAD Change Since Last Visit	 Started  Stopped  No Change  Dose Change : _____

SECTION 6: REDO PROCEDURE – see APPENDIX F REDO PROCEDURAL CRF

Variable	Data Entry
Redo Procedure	 No  Yes (Date : _____)

CONFIDENTIAL

Form Completed By: _____ **Date:** _____

17. Appendix F – Redo Procedural CRF**SECTION 1: DEMOGRAPHICS AND CLINICAL HISTORY/DATA**

Variable	Data Entry
Date of Procedure	_____
Patient MRN	_____
Age / Gender	_____ years  Male  Female
Height	_____ cm
Weight	_____ kg
BMI	_____ kg/m ²
Type of Arrhythmia	 Paroxysmal AF  Persistent AF  Atrial Flutter : _____
Index Ablation	 PVI  Roof Line  Posterior Wall Isolation (PWI)  Cavotricuspid Isthmus (CTI)  Mitral Isthmus Line  Other: _____
Operator 1 Operator 2	

CHA2DS2-VASc Score

CONFIDENTIAL

Risk Factor	Points	Check if Present
Congestive Heart Failure	1	
Hypertension	1	
Age ≥ 75 years	2	
Diabetes Mellitus	1	
Stroke / TIA / Thromboembolism	2	
Vascular Disease	1	
Age 65 - 74 years	1	
Sex Category (Female)	1	
TOTAL SCORE		____ / 9

Echocardiography Parameters

Variable	Entry
Date of Echo	____ / ____ / ____
LVEF (%)	_____
LA Diameter (mm)	_____
LA Volume (ml)	_____
LA Volume Indexed (ml/m ²)	_____
RA Enlargement	 None  Mild  Moderate  Severe
Mitral Regurgitation	 None  Mild  Moderate  Severe

Antiarrhythmic Drug (AAD) History

(Check all currently or recently used)

☐ Amiodarone ☐ Flecainide ☐ Propafenone ☐ Dronedarone ☐ Other: _____

SECTION 2: PHASE 1 - PRE-ABLATION MAPPING

(Both maps must be acquired during CS pacing or in arrhythmia if patient is in flutter, with a fill threshold 3mm)

Catheter	LA Map Completed?	Fill Threshold \leq 3mm Achieved?	Total Number of Points
Octaray	 Yes  No	 Yes  No	_____ points
Optrell bipolar	 Yes  No	 Yes  No	_____ points
Optrell multipolar	 Yes  No	 Yes  No	_____ points

Catheter	RA Map Completed?	Fill Threshold \leq 3mm Achieved?	Total Number of Points
Octaray	 Yes  No	 Yes  No	_____ points
Optrell bipolar	 Yes  No	 Yes  No	_____ points
Optrell multipolar	 Yes  No	 Yes  No	_____ points

Durably Isolated PVs	 Yes  No : _____
-----------------------------	--

SECTION 3: PHASE 2 – PRIOR LINE CONDUCTION BLOCK ASSESSMENT

(Complete this sub-section for EVERY prior linear lesion. See Section 3b, 3c and 3d. Duplicate if necessary.)

Line Checked	 Roof Line  Posterior Wall Isolation (PWI)  Cavotricuspid Isthmus (CTI)  Mitral Isthmus Line  Other: _____
---------------------	--

CONFIDENTIAL

Assessment Method	Time to Verify Block	Block Confirmed?
Optrell Vector Assessment (time to assess block by moving the catheter across the line to review vectors)	____ min : ____ sec	 Yes  No
Octaray Activation Mapping (time to create an activation map sufficient to determine presence or absence of block)	____ min : ____ sec	 Yes  No

Concordance for this line: ☐Yes (Methods agree) ☐No (Methods disagree)

Explain: _____

SECTION 4: PHASE 3 - ABLATION DETAILS

Variable	Data Entry
Ablation Energy Used	 RFA  PFA
Redo PVI Performed?	 Yes  No
PVI Successfully Achieved?	 Yes  No
Linear Lesions Created (Check all that apply)	 Roof Line  Posterior Wall Isolation (PWI)  Cavotricuspid Isthmus (CTI)  Mitral Isthmus Line  Other: _____

SECTION 5: PHASE 4 - CONDUCTION BLOCK ASSESSMENT

(Complete this sub-section for EVERY linear lesion created. See Section 5b, 5c and 5d. Duplicate if necessary.)

Line Checked	 Roof Line  Posterior Wall Isolation (PWI)  Cavotricuspid Isthmus (CTI)  Mitral Isthmus Line  Other: _____
Ablation Energy Used	 RFA  PFA

Assessment Method	Time to Verify Block	Block Confirmed?
Optrell Vector Assessment (time to assess block by moving the catheter across the line to review vectors)	____ min : ____ sec	 Yes  No
Octaray Activation Mapping (time to create an activation map sufficient to determine presence or absence of block)	____ min : ____ sec	 Yes  No

Concordance for this line: ☐Yes (Methods agree) ☐No (Methods disagree)

Explain:_____

SECTION 5: ACUTE PROCEDURAL COMPLICATIONS (completed at hospital discharge)

Variable	Data Entry
None	
Pericardial Effusion / Tamponnade	
Stroke / TIA	
Vascular Complication requiring intervention	

CONFIDENTIAL

Variable	Data Entry
Phrenic Nerve Injury	
Prolongation of Hospitalization (>24 hours beyond the expected post-procedural course)	
Esophageal injury	
Heart failure exacerbation requiring treatment	
Other :	<hr/>

Form Completed By: _____ **Date:** _____

Investigator Signature: _____ **Date:** _____

SECTION 3b: PHASE 2 - PRIOR LINE CONDUCTION BLOCK ASSESSMENT

Line Checked	 Roof Line  Posterior Wall Isolation (PWI)  Cavotricuspid Isthmus (CTI)  Mitral Isthmus Line  Other: _____
---------------------	--

Assessment Method	Time to Verify Block	Block Confirmed?
Optrell Vector Assessment (time to assess block by moving the catheter across the line to review vectors)	____ min : ____ sec	 Yes  No
Octaray Activation Mapping (time to create an activation map sufficient to determine presence or absence of block)	____ min : ____ sec	 Yes  No

Concordance for this line: ☐Yes (Methods agree) ☐No (Methods disagree)

Explain: _____

SECTION 3c: PHASE 2 - PRIOR LINE CONDUCTION BLOCK ASSESSMENT

Line Checked	 Roof Line  Posterior Wall Isolation (PWI)  Cavotricuspid Isthmus (CTI)  Mitral Isthmus Line  Other: _____
---------------------	--

Assessment Method	Time to Verify Block	Block Confirmed?
Optrell Vector Assessment (time to assess block by moving the catheter across the line to review vectors)	___ min : ___ sec	 Yes  No
Octaray Activation Mapping (time to create an activation map sufficient to determine presence or absence of block)	___ min : ___ sec	 Yes  No

Concordance for this line: ☐Yes (Methods agree) ☐No (Methods disagree)

Explain: _____

SECTION 3d: PHASE 2 - PRIOR LINE CONDUCTION BLOCK ASSESSMENT

Line Checked	 Roof Line  Posterior Wall Isolation (PWI)  Cavotricuspid Isthmus (CTI)  Mitral Isthmus Line  Other: _____
---------------------	--

Assessment Method	Time to Verify Block	Block Confirmed?
Optrell Vector Assessment (time to assess block by moving the catheter across the line to review vectors)	___ min : ___ sec	 Yes  No
Octaray Activation Mapping (time to create an activation map sufficient to determine presence or absence of block)	___ min : ___ sec	 Yes  No

CONFIDENTIAL

Concordance for this line: ☐Yes (Methods agree) ☐No (Methods disagree)

Explain:_____

SECTION 5b: PHASE 4 - CONDUCTION BLOCK ASSESSMENT

Line Checked	 Roof Line  Posterior Wall Isolation (PWI)  Cavotricuspid Isthmus (CTI)  Mitral Isthmus Line  Other: _____
Ablation Energy Used	 RFA  PFA

Assessment Method	Time to Verify Block	Block Confirmed?
Optrell Vector Assessment (time to assess block by moving the catheter across the line to review vectors)	____ min : ____ sec	 Yes  No
Octaray Activation Mapping (time to create an activation map sufficient to determine presence or absence of block)	____ min : ____ sec	 Yes  No

Concordance for this line: ☐Yes (Methods agree) ☐No (Methods disagree)

Explain:_____

SECTION 5c: PHASE 4 - CONDUCTION BLOCK ASSESSMENT

Line Checked	 Roof Line  Posterior Wall Isolation (PWI)  Cavotricuspid Isthmus (CTI)  Mitral Isthmus Line  Other: _____
Ablation Energy Used	 RFA  PFA

CONFIDENTIAL

Assessment Method	Time to Verify Block	Block Confirmed?
Optrell Vector Assessment (time to assess block by moving the catheter across the line to review vectors)	____ min : ____ sec	 Yes  No
Octaray Activation Mapping (time to create an activation map sufficient to determine presence or absence of block)	____ min : ____ sec	 Yes  No

Concordance for this line: ☐Yes (Methods agree) ☐No (Methods disagree)

Explain:_____

SECTION 5d: PHASE 4 - CONDUCTION BLOCK ASSESSMENT

Line Checked	 Roof Line  Posterior Wall Isolation (PWI)  Cavotricuspid Isthmus (CTI)  Mitral Isthmus Line  Other: _____
Ablation Energy Used	 RFA  PFA

Assessment Method	Time to Verify Block	Block Confirmed?
Optrell Vector Assessment (time to assess block by moving the catheter across the line to review vectors)	____ min : ____ sec	 Yes  No
Octaray Activation Mapping (time to create an activation map sufficient to determine presence or absence of block)	____ min : ____ sec	 Yes  No

CONFIDENTIAL

Assessment Method	Time to Verify Block	Block Confirmed?

Concordance for this line: ☐Yes (Methods agree) ☐No (Methods disagree)

Explain:_____
